2.2 Analysis sets

The screened set (SCR) will include all patients who provided informed consent.

The randomized set (RAN) will include all patients that were randomized. Data from these patients will be analyzed according to the treatment to which the patient was assigned at randomization.

The full analysis set (FAS) will include all randomized patients who received at least one dose of study treatment. It was considered reasonable to limit the FAS to patients who took study treatment, because the decision on whether or not treatment is started will not be influenced by the treatment group assignment due to the effective treatment blinding procedures described in protocol Section 5.4. Following the intent-to-treat principle, patients will be analyzed according to the treatment they were assigned to at randomization.

The safety set (SAF) will include all patients who received at least one dose of study treatment. Patients will be analyzed according to the treatment they received.

The analysis of the primary objective will be performed on the FAS. The FAS will be used for the analysis of all other efficacy variables. The SAF will be used in the analysis of all safety variables.

If an incorrect randomization stratum is inadvertently selected for a patient by the investigator in the IRT, patients will still be included in all analyses. The corrected stratum information as per the CRF data will be used in any analysis models.

2.2.1 Subgroup of interest

NA

2.3 Patient disposition, demographics and other baseline characteristics

2.3.1 Patient disposition

The following summaries will be provided overall and by treatment group: % based on the total number of RAN patients:

- Number of screened patients
- Number (%) of patients who were randomized
- Number (%) of patients who were randomized but not treated
- Number (%) of patients who were treated
- Number (%) of patients who discontinued the study treatment phase
- Primary reason for study treatment phase discontinuation
- Number (%) of patients who have discontinued the study
- Reasons for discontinuation from the study

Patient randomization numbers and whether they completed or discontinued from the study will be listed, with date of last dose and primary reason for discontinuation, including the unblinding date if applicable.

2.3.2 Protocol Deviations

The number of subjects with protocol deviations will be tabulated by category and deviation for the RAN. Protocol deviations will be listed with date and study day of occurrence and deviation.

2.3.3 Analysis sets

The number of subjects included in each analysis set will be tabulated. Reasons for exclusions from analysis sets will be tabulated for RAN. Patient exclusion from analysis sets will be listed for all patients with reasons for exclusion (including protocol deviations).

2.3.4 Demographics and baseline characteristics

Demographics and baseline characteristics will be summarized by treatment group using the FAS set. Summaries will include age, gender, race, ethnicity, height, weight, BMI, pre- and post-bronchodilator FEV₁, percent predicted FEV₁, FEV₁ reversibility, duration of asthma, number of asthma exacerbations in prior year, smoking history (never/former), number of pack years, baseline ACQ-5, baseline AQLQ+12 and Peripheral blood eosinophils. Continuous variables will be summarized using descriptive statistics (number of non-missing data, mean, standard deviation, median, first and third quartiles, minimum, and maximum) and categorical variables will be summarized in terms of the number and percentage of patients in each category including a category for missing data if any for the treatment group.

Blood eosinophil counts will also be summarized for the SCR. The baseline blood eosinophil will be considered as the eosinophil value at Visit 1. If the value at Visit 1 is missing then the baseline value will be considered as the first assessment after Visit 1 and prior to first dose of study medication, unless there is no value before randomization, in which situation, it will be missing.

Background asthma therapy will be categorized into GINA steps and will be summarized at baseline.

No statistical analyses will be provided for baseline comparability among the treatment groups.

Derivation of the demographics and baseline characteristics

- BMI is calculated as: $BMI (kg/m^2) = Weight (kg) / [Height (m) * Height (m)]$
- Duration of asthma is calculated from the date of asthma first diagnosed recorded on the eCRF until the 1st visit. If the date is missing in day and/or month, it will be imputed as follows. If the year is before the first visit, the missing days will be imputed as the first of the month and the missing months will be imputed as July. If the year is the current year of the first visit, the missing days will be imputed as the first of the month and the missing months will be imputed as January.

Medical history

Medical history will be coded with the Medical Dictionary for Regulatory Activities terminology (MedDRA) using the most recent version at the time of database lock. History/conditions as well as protocol solicited events for asthma will be summarized for the FAS set by primary system organ class and preferred term. Verbatim recorded history/conditions will be listed together with the coded terms, date of diagnosis/surgery and whether the problem was ongoing at start of the study.

2.4 Treatments (study treatment, rescue medication, concomitant therapies, compliance)

2.4.1 Study treatment / compliance

Since the study has a double dummy design, each patient will be dispensed two bottles of study medication at the dispensing visits. Bottle 1 has study medication corresponding to 150 mg QAW039 or placebo and Bottle 2 has study medication corresponding to 450 mg QAW039 or placebo. Exposure will be presented on the SAF. Exposure will be presented for each treatment while compliance will be presented by treatment arm for each of the bottles separately.

2.4.1.1 Duration of exposure

Duration of exposure to a treatment will be calculated as the number of days between the first dose date and the last dose date exposed to that treatment over the specified period (expressed as: $Duration\ of\ exposure\ (weeks) = (Date\ of\ last\ known\ dose\ of\ study\ drug - Date\ of\ first\ dose\ of\ study\ drug + 1) / 7$). The duration of exposure will be summarized by treatment group for the safety set as a continuous variable with the standard descriptive statistics.

In addition, the duration of exposure and cumulative exposure will be summarized as a categorical variable classified into ≤ 4 weeks, $> 4 - 12$ weeks, $> 12 - 20$ weeks, $> 20 - 28$ weeks, $> 28 - 36$ weeks, $> 36 - 44$ weeks, > 44 weeks or ≥ 4 weeks, ≥ 12 weeks, ≥ 20 weeks, ≥ 28 weeks, ≥ 36 weeks, ≥ 44 weeks, ≥ 52 weeks, respectively.

Dose administration data will be listed for patients in the SAF.

2.4.1.2 Compliance

NA

2.4.2 Prior, concomitant and post therapies

Medications started and stopped prior to study drug and taken concomitantly will be summarized by treatment group in separate tables in the SAF. The medication will be classified into “prior”, “concomitant” based on the start/end dates.

Prior: Any medication with a start date before Day 1.

Concomitant: Any medication with end date on or after Day 1 or ongoing at the end of trial or missing end date and start date before the end of the Treatment Epoch.

Medications can be considered both prior and concomitant.

Concomitant therapies will be recorded and summarized separately for asthma related medications and other medications. Concomitant therapies will be recorded and summarized separately for asthma related medications and other medications. Concomitant asthma related medications will be summarized by pre-defined category. Concomitant medications not related to asthma will be summarized by pharmacological (ATC) class and preferred term. More than one ATC class per medication is possible and the medication will be reported under all applicable classes.

Short acting beta2 agonist (SABA) rescue medication usage (mean number of puffs) during the screening/run-in period will be summarized. Patients taking prohibited concomitant medications will be noted in the summary of protocol deviations.

All summaries will be by treatment group on the Safety Set.

2.5 Analysis of the primary objective

2.5.1 Primary endpoint

The primary endpoint for this study is total systemic corticosteroid dose in mg prednisone/prednisolone (or equivalent) over 52 weeks of treatment. The primary endpoint is analysed using FAS.

2.5.2 Statistical hypothesis, model, and method of analysis

The primary endpoint will be analyzed in subpopulation of patients with eosinophil count ≥ 250 cells/ μ l and in overall population. The primary null hypotheses are:

- H_{01} 450 eosinophil subgroup: the distribution of the total systemic corticosteroid dose in mg prednisone/prednisolone (or equivalent) in Fevipirant 450 mg QD plus SoC is equivalent

to the distribution of the total systemic corticosteroid dose in mg prednisone/prednisolone (or equivalent) in placebo plus SoC in patients with eosinophil count ≥ 250 cells/ μ l

[figure not shown]
- H₀₂ 150 eosinophil subgroup: the distribution of the total systemic corticosteroid dose in mg prednisone/prednisolone (or equivalent) in Fevipiprant 150 mg QD plus SoC is equivalent to the distribution of the total systemic corticosteroid dose in mg prednisone/prednisolone (or equivalent) in placebo plus SoC in patients with eosinophil count ≥ 250 cells/ μ l
- H₀₃ 450 overall population: the distribution of the total systemic corticosteroid dose in mg prednisone/prednisolone (or equivalent) in Fevipiprant 450 mg QD plus SoC is equivalent to the distribution of the total systemic corticosteroid dose in mg prednisone/prednisolone (or equivalent) in placebo plus SoC for the overall population
- H₀₄ 150 overall population: the distribution of the total systemic corticosteroid dose in mg prednisone/prednisolone (or equivalent) in Fevipiprant 150 mg QD plus SoC is equivalent to the distribution of the total systemic corticosteroid dose in mg prednisone/prednisolone (or equivalent) in placebo plus SoC for the overall population

The primary alternate hypotheses are:

- H_{A1} 450 eosinophil subgroup: the distribution of the total systemic corticosteroid dose in mg prednisone/prednisolone (or equivalent) in Fevipiprant 450 mg QD plus SoC is different to the distribution of the total systemic corticosteroid dose in mg prednisone/prednisolone (or equivalent) in placebo plus SoC in patients with eosinophil count ≥ 250 cells/ μ l
- H_{A2} 150 eosinophil subgroup: the distribution of the total systemic corticosteroid dose in mg prednisone/prednisolone (or equivalent) in Fevipiprant 150 mg QD plus SoC is different to the distribution of the total systemic corticosteroid dose in mg prednisone/prednisolone (or equivalent) in placebo plus SoC in patients with eosinophil count ≥ 250 cells/ μ l
- H_{A3} 450 overall population: the distribution of the total systemic corticosteroid dose in mg prednisone/prednisolone (or equivalent) in Fevipiprant 450 mg QD plus SoC is different to the distribution of the total systemic corticosteroid dose in mg prednisone/prednisolone (or equivalent) in placebo plus SoC for the overall population
- H_{A4} 150 overall population: the distribution of the total systemic corticosteroid dose in mg prednisone/prednisolone (or equivalent) in Fevipiprant 150 mg QD plus SoC is different to the distribution of the total systemic corticosteroid dose in mg prednisone/prednisolone (or equivalent) in placebo plus SoC for the overall population

Familywise type I error rate control

The familywise type I error rate will be controlled at the two-sided 5% level across the primary null hypotheses using graphical approach specified by [Figure 2-1 \(Bretz et al 2009\)](#).

Figure 2-1 Closed testing procedure for primary objectives

Vertices with associated weights denote the individual null hypotheses and their local significance levels (initially the alpha is split 50%:50% across the primary null hypotheses regarding the subgroup with blood eosinophils ≥ 250 cells/ μl for the 2 fevipiprant doses). Directed edges between the vertices specify how the local significance levels are propagated in case of significant results.

Initially, 50% of the alpha is assigned to each of the primary null hypotheses regarding the subgroup with blood eosinophils ≥ 250 cells/ μl for the Fevipiprant 450 mg QD and Fevipiprant 150 mg QD doses, respectively. Once this first primary null hypothesis for a dose has been rejected, the alpha will be distributed to the other null hypothesis regarding the overall population for the same dose. If the null hypothesis regarding the primary endpoint for the overall population is rejected for a dose, then alpha is reassigned to the primary null hypotheses regarding the subgroup with blood eosinophils ≥ 250 cells/ μl for the other dose. Alpha will only be reassigned from the null hypotheses for a dose to the null hypotheses for the other dose once all null hypotheses for the dose to which the alpha was originally assigned have been rejected.

Statistical model for primary variable

The total systemic corticosteroid dose in mg prednisone/prednisolone (or equivalent) over 52 weeks of treatment will be analyzed using the Wilcoxon-Mann-Whitney rank sum test (Van Elteren test). For overall population analysis will be stratified by randomization stratum – blood eosinophils levels (≥ 250 cells/ μl and < 250 cells/ μl). For subgroup with blood eosinophils ≥ 250 cells/ μl , analysis will not include stratification factor. The summary statistics for total SCS dose by treatment group will be provided.

The primary estimand will quantify the treatment effect based on on-treatment data. The total SCS dose data will be aggregated into monthly data for analysis. The primary estimand will account for different post-randomization events as follows:

- Use of rescue medications: Efficacy data collected during use of rescue medication will be used for analysis.

- Early discontinuation of study drug (prior to completing 52 weeks of treatment period): For the patients discontinuing study drug early, the total SCS dose for 52 weeks will be obtained as annualized SCS dose. For example if patient took 280 mg for 7 months then for 12 months patient will be taking $280 \times 12/7 = 480$ mg total SCS dose.
- Use of biologics prior to discontinuation of treatment: Efficacy data collected during the use of biologics will be set to missing, since use of biologics can confound efficacy data. Biologics are usually taken for long period of time. Thus, after replacing SCS dose with missing, patient will not have data available for remaining duration of the study. The total SCS dose will be obtained as annualized dose as explained above.

2.5.3 Handling of missing values/censoring/discontinuations

Some patients may discontinue early and may not complete the entire study duration. For the patients discontinuing treatment early, the total SCS dose for 52 weeks will be obtained as annualized SCS dose. For example if patient took 280 mg for 7 months then for 12 months patient will be taking $280 \times 12/7 = 480$ mg total SCS dose. Efficacy data collected during the use of biologics will be set to missing, since use of biologics can confound efficacy data. After replacing SCS dose with missing, patient will not have data available for all 12 months, thus total SCS dose will be obtained as annualized dose.

-

2.6 Analysis of the key secondary objective

There is no key secondary objective.

2.7 Analysis of secondary efficacy objective(s)

2.7.1 Secondary endpoints

2.7.1.1 Proportion of patients with no SCS use over 52 weeks of treatment or during on-treatment period

The proportion of patients with no SCS use in individually observed on-treatment time will be presented. Patients will be considered as non-responders if patient takes SCS dose in observed period of treatment.

2.7.1.2 Proportion of patients requiring ≥ 7.5 mg systemic corticosteroid dose in mg prednisone/prednisolone (or equivalent) per day continuously for at least 30 days

This is a composite endpoint where patients requiring ≥ 7.5 mg systemic corticosteroid dose in mg prednisone/prednisolone (or equivalent) per day continuously for at least 30 days in 52 weeks treatment period or during on-treatment period are considered as responders. Patients will be considered as non-responders if patient do not satisfy either of the conditions.

2.7.1.3 Summary of Change from baseline in Asthma Related Quality of Life Questionnaire (AQLQ+12) total score during on-treatment period

The 32 items in the AQLQ+12 are divided into 4 domain-specific scores and a total score as follows:

- Symptoms = Mean of Items 6, 8, 10, 12, 14, 16, 18, 20, 22, 24, 29, 30 (12 items)
- Activity limitation = Mean of Items 1, 2, 3, 4, 5, 11, 19, 25, 28, 31, 32 (11 items)
- Emotional function = Mean of Items 7, 13, 15, 21, 27 (5 items)
- Environmental Stimuli = Mean of Items 9, 17, 23, 26 (4 items)
- Overall Score = Mean of Items 1 to 32 (32 items)

Each item of the AQLQ+12 is equally weighted and scored along a 7-point scale, where 1 indicates maximal impairment and 7 indicates no impairment. Thus, higher scores indicate better asthma-related HRQOL (Health-Related Quality of Life). There is a mean score calculated for each of the four domains, as well as an overall quality-of-life score, which is the mean score of all 32 items. The resultant overall scores will be between 1 and 7.

The developer suggests no more than 10% of missing data. This means no more than 3 missing responses for the overall score and no more than 1 missing response per domain. For the symptoms and activity domain scores, one missing value per domain is allowed. For the emotional function and environmental stimuli domain scores, no missing values are allowed. If these limits for missing questions are exceeded, the variable will be considered missing and will be imputed as described in [Section 2.7.3](#).

The minimal important difference (MID), defined as “the smallest difference in score which patients perceive as beneficial and would mandate, in the absence of troublesome side effects and excessive cost, a change in the patient’s management,” of 0.5 has been established for this questionnaire as clinically significant ([Juniper, et al 1994](#)).

2.7.1.4 Summary of change from baseline of Asthma Control Questionnaire (ACQ-5) total score during on-treatment period

In this study, the ACQ-5 will be used to assess improvements in asthma symptom control. The original ACQ consists of 7 items: 5 items on symptom assessment, 1 item on rescue bronchodilator use, and 1 item on airway calibre (% FEV1 predicted). As the Spirometry assessments are performed centrally, the rescue bronchodilator use and % FEV1 predicted are not included in the version of ACQ chosen for this study.

The ACQ-5 will be self-administered at the clinic and it only takes a few minutes to complete. Patients will be asked to recall how their asthma has been during the previous week and to respond to the symptom questions on a 7-point scale (0=no impairment, 6=maximum impairment). The questions are equally weighted and the ACQ-5 score is the mean of the 5 questions and therefore between 0 (totally controlled) and 6 (severely uncontrolled) ([Juniper et al 1999](#); [Juniper et al 2005a](#)).

A score of 1.5 at baseline indicates patients who entered the study had inadequately controlled asthma ([Juniper et al 2006](#)). In addition, the minimal important difference (MID) or smallest change that can be considered clinically important is 0.5.

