9.5 Analysis of secondary variables

9.5.1 Efficacy variables

Proportion of patients with no SCS use over 52 weeks of treatment

The proportion of patients with no SCS use over 52 weeks treatment will be summarized by treatment and analyzed using logistic regression in overall population. The model will include treatment and randomization strata as covariates. Estimates of the odds ratio between treatment groups will be displayed along with associated 95% confidence intervals and two-sided p-values.

Proportion of patients requiring ≥ 7.5 mg systemic corticosteroid dose in mg prednisone/prednisolone (or equivalent) per day continuously for at least 30 days

The proportion of patients requiring ≥ 7.5 mg systemic corticosteroid dose in mg prednisone/prednisolone (or equivalent) per day continuously for at least 30 days in 52 weeks treatment period will be summarized by treatment and analyzed using logistic regression in overall population. The model will include treatment and randomization strata as covariates. Estimates of the odds ratio between treatment groups will be displayed along with associated 95% confidence intervals and two-sided p-values.

Asthma Quality of Life Questionnaire (AQLQ+12)

The 32 items in the AQLQ are divided into 4 domain- specific scores and a total score as follows:

- Symptoms = Mean of Items 6,8,10,12,14,16,18,20,22,24,29,30 (12 items)

- Activity limitation = Mean of Items 1,2,3,4,5,11,19,25,28,31,32 (11 items)
- Emotional function = Mean of Items 7,13,15,21,27 (5 items)
- Environmental stimuli = Mean of Items 9,17,23,26 (4 items)
- Overall score = Mean of Items 1 to 32 (32 items)

Each item of the AQLQ is equally weighted and scored along a 7-point scale, where 1 indicates maximal impairment and 7 indicates no impairment. Thus, higher scores indicate better asthma-related HRQOL. There is a mean score calculated for each of the four domains, as well as an overall quality of life score, which is the mean score of all 32 items. The resultant overall scores will be between 1 and 7.

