2.7.1.5 Proportion of patients with prescription of biologic treatment

The proportion of patients with any prescription of biologic therapy during the on-treatment period will be presented. Events which occur during on-treatment period will be included.

2.7.1.6 Summary of change from baseline of daytime and nighttime symptom scores by 4-week intervals during on-treatment period

The daytime and night time symptom scores will be collected using validated electronic patient diary. Scoring of measures: A range of response categories for each question from 0 to 6 (0 – totally controlled, 6 – extremely poorly controlled) is used in the daytime asthma symptom scale. Response categories ranging from 0 (indicating no awakening with asthma symptoms) to 3 (indicating awake all night) are used in the nocturnal diary scale. Daily daytime symptom scores will be computed as the average of the available scores on four questions on the daytime symptom scale.

The mean daytime asthma symptom scores/nighttime symptom score will be calculated for each patient for each 4 week visit interval and over on-treatment period. The average score for each time interval is defined as the sum of daily scores (based on all the available questions) divided by the number of days where diary records have been made on nighttime/daytime score for that visit interval. The non-missing data within each 4 week interval in treatment period will be used to calculate the mean value, as long as there are at least 14 days with non-missing e-diary data (based on all the available questions) in a 4-week period. Otherwise, the value will be set as missing.

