2.7.2 Statistical hypothesis, model, and method of analysis

The analysis of all secondary endpoints will be based on on-treatment data (that is from first dose of study treatment till last dose of study treatment + 1).

The proportion of patients with no SCS use during on-treatment will be summarized by treatment groups.

The proportion of patients requiring ≥ 7.5 mg systemic corticosteroid dose in mg prednisone/prednisolone (or equivalent) per day continuously for at least 30 days within the on-treatment period will be summarized by treatment in overall population.

AQLQ+12, ACQ-5 and change from baseline in daytime and nighttime score will be summarized by treatment for all visits. All the summaries will be based on observed on-treatment data and non-imputed data.

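### In a trial stopped early, SAP 2.7.1 reports SCS-free use, 30-day high-dose use and biologic prescription only as crude proportions over unequal on-treatment time, so none estimates a risk at a common time point

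*SAP*

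**What the plan says.** **Listed endpoints.** SAP 1.2 gives the SCS-free proportion a 52-week window and defines the biologic endpoint as a time to first prescription over 52 weeks. The 30-day high-dose endpoint has no window in SAP 1.2, but protocol 9.5.1 gives it one: "per day continuously for at least 30 days in 52 weeks treatment period will be summarized by treatment". Protocol 9.5.1 planned logistic regression for the two proportions and Cox regression for the biologic endpoint.

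**Planned summaries.**
- SCS-free (SAP 2.7.1.1): "The proportion of patients with no SCS use in individually observed on-treatment time will be presented". The heading signals the window: "Proportion of patients with no SCS use over 52 weeks of treatment or during on-treatment period".
- 30-day use at 7.5 mg/day or more (SAP 2.7.1.2): patients with such use "per day continuously for at least 30 days in 52 weeks treatment period or during on-treatment period are considered as responders". For everyone else, "Patients will be considered as non-responders if patient do not satisfy either of the conditions".
- Biologics (SAP 2.7.1.5): "The proportion of patients with any prescription of biologic therapy during the on-treatment period will be presented".

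**Data basis.** SAP 2.7.2 states: "The analysis of all secondary endpoints will be based on on-treatment data", defined as "from first dose of study treatment till last dose of study treatment + 1". SAP 2.7.3, whose heading covers censoring, says only that nothing is imputed.

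**Disclosure.** SAP 4 reports the early stop, the immaturity of the data and the move to descriptive analysis of all secondary endpoints. SAP 2.4.1.1 tabulates exposure by arm separately.

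**The concern.** Each of the three proportions counts whether an event happened during a patient's own time on treatment, and that time varies. A patient seen for two months without SCS counts the same as one seen for twelve. A patient with under 30 days on treatment cannot complete a 30-day run inside the on-treatment window, yet counts as not meeting the criterion.

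The figures therefore mix follow-up lengths and describe neither the 52-week quantity nor the risk at any other stated time. A reader who sets them beside the endpoints in SAP 1.2 could take them for 52-week results. What is at stake is interpretation of three listed endpoints. SAP 4 also does not record that a time-to-event endpoint became a proportion, or that a fixed window became a variable one.

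**Working it through.** The documents state no figure for these crude proportions and give no follow-up times, so there is nothing to reproduce. The direction follows by logic; the sizes need assumptions.

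**Direction.** Shortening a patient's window can only remove SCS courses, 30-day runs or prescriptions. It can never add one. So SCS-free is overstated against 52 weeks and the other two are understated.

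**Inputs for SCS-free.** The class percentages come from SAP section 3, Table 3.2 (planning scenario for eosinophils of 250 cells/µl or more, used here as a proxy for the overall population):
- placebo: 42.7 / 8.8 / 13.5 / 8.4 / 6.6 / 20.0%
- fevipiprant: 60 / 15 / 9 / 3 / 3 / 10%

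The lowest class (0-50 mg) stands in for no SCS use, so the 12-month values are 42.7% and 60%, a difference of 17.3 points.

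**Assumptions.** A patient in class c has k_c courses at independent uniform times over 12 months. Three sets of k_c are used: base 0/1/1/2/3/5, more courses 0/1/2/3/4/6, and one course per user 0/1/1/1/1/1. Follow-up T is uniform from a to b months.

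**Formula.** P(no course by T) = Σ p_c (1 − T/12)^k_c. For k ≥ 1, the average of (1 − T/12)^k over a to b is 12[(1 − a/12)^(k+1) − (1 − b/12)^(k+1)] / [(k+1)(b − a)].

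*Example, base, 0-3 months.* The averages are 0.875 (k=1), 0.7708 (k=2), 0.6836 (k=3) and 0.548 (k=5).
- Placebo: 0.427 + 0.223×0.875 + 0.084×0.7708 + 0.066×0.6836 + 0.2×0.548 = 0.842.
- Fevipiprant: 0.60 + 0.24×0.875 + 0.03×0.7708 + 0.03×0.6836 + 0.10×0.548 = 0.908.
- Difference: 6.7 points before rounding.

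| Follow-up (months) | 9-12 | 6-12 | 0-12 | 0-6 | 0-3 |
|---|---|---|---|---|---|
| Crude placebo SCS-free %, base | 45.7 | 49.3 | 61.6 | 74.0 | 84.2 |
| more courses | 44.1 | 46.4 | 57.9 | 69.3 | 80.5 |
| one course | 49.9 | 57.0 | 71.4 | 85.7 | 92.8 |
| Arm difference (12-month 17.3), base | 17.4 | 17.1 | 13.8 | 10.5 | 6.7 |
| more courses | 18.0 | 18.2 | 15.4 | 12.6 | 8.4 |
| one course | 15.1 | 13.0 | 8.7 | 4.3 | 2.2 |

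**Other two endpoints, share of the 12-month proportion captured.**
- 30-day use: completion of the run is assumed uniform from m = 30/30.4375 = 0.986 to 12 months, and the share is the mean of max(0, (T − m)/(12 − m)). For the five windows this gives 86, 73, 46, 19 and 6%. Patients with under 30 days make up 0, 0, 8, 16 and 33%.
- Biologic prescription: time is assumed uniform over 12 months, and the share is the mean of T/12. This gives 88, 75, 50, 25 and 13%.

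**Unequal follow-up, no drug effect.** The placebo distribution is used in both arms, with one month less average follow-up in one arm. Spurious SCS-free difference in points:

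| Windows compared (months) | base | more courses | one course |
|---|---|---|---|
| 9-12 v 8-11 | 2.2 | 1.2 | 4.8 |
| 6-12 v 5-11 | 2.6 | 1.8 | 4.8 |
| 0-12 v 0-10 | 3.4 | 2.9 | 4.8 |
| 0-6 v 0-4 | 6.3 | 6.8 | 4.8 |
| 1-3 v 0-2 | 9.3 | 11.1 | 4.8 |

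**Cross-check with a different model.** Under a constant hazard with 39.2% SCS-free at 52 weeks (one of the three zero-dose shares in SAP Table 3.1), S(w) = 0.392^(w/52). This is 80.6% at 12 weeks, 69.8% at 20 and 62.6% at 26. Exposure of 20 v 26 weeks alone gives about 7 points.

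**The case against.** Much of this is disclosed. SAP 4 says the data are too immature for the protocol analyses and that secondary endpoints become descriptive. The SAP 2.7.1 headings name the on-treatment window and the biologic proportion, and exposure is tabulated by arm. An observed proportion labelled as such does not claim to be a 52-week risk. This stands, and it rules out any reading that the change was concealed. What it leaves open is narrow: SAP 4 does not mention the changed window or the replaced biologic endpoint, and a separate exposure table does not let a reader recover a risk at a common time.

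A reader might also infer that the crude proportions favour the drug. The documents do not support that. With equal follow-up the arm difference is mostly compressed; in the more-courses variant it slightly exceeds 17.3 points for the two longest windows. A spurious difference needs unequal or informative on-treatment time. Allocation is 1:1:1 and blinded, so a sponsor-level stop gives no reason in itself to expect that.

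A third tempting reading is that Kaplan-Meier would remove the whole gap to the 52-week value. It would not. With follow-up uniform over 1-12 months (mean 6.5), the base-case crude value is 58.7%. That is only 1.3 points from the true 6-month value of 57.4% (0.427 + 0.5×0.223 + 0.25×0.084 + 0.125×0.066 + 0.03125×0.2). The gain is a defined common time point, and a 52-week estimate may not be supported.

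**Conclusion.** The concern holds as a point of description and interpretation. Followed as written, SAP 2.7.1.1, 2.7.1.2 and 2.7.1.5 give three proportions that estimate no risk at a common time. The direction against 52 weeks is certain: SCS-free too high, 30-day high-dose use and biologic prescription too low.

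The size depends on follow-up and event timing, which the documents do not give. In the illustration, 42.7% SCS-free at 12 months reads as about 44-50% with 9-12 months of follow-up and 80-93% with 0-3 months. The 17.3-point difference reads as 15-18 and 2-8 points respectively. One month less average follow-up in one arm, with no drug effect, is worth about 1 to 7 points, or 5 to 11 if follow-up is only a few months. These figures rest on the assumed course counts, uniform event times and follow-up windows, and on planning classes for the high-eosinophil subgroup.

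No test or alpha depends on these endpoints. This is a cheap improvement that should be made before reporting; it does not threaten the trial's inference.

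**What to change.** 1. In SAP 2.7.1.1, 2.7.1.5 and 2.7.2, add descriptive Kaplan-Meier (or cumulative incidence) estimates by arm for time to first SCS use and time to first biologic prescription. Censor at the end of the SAP 2.7.2 on-treatment window. Show numbers at risk, and give 95% CIs only at time points the follow-up supports.
2. State how the start of a biologic is handled in the SCS curve, since SAP 2.7 is silent. Protocol 5.5.5 allows biologics as step-up for uncontrolled patients, so censoring there may be informative.
3. Keep all three crude proportions, including the 30-day one. Label them *observed on-treatment time only* and put follow-up by arm beside them.
4. Record in SAP 4 that the 52-week window changed and that the time-to-event biologic endpoint was replaced by a proportion.

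Optional: a curve for the 30-day endpoint, SCS curves with and without censoring at biologic start, and a curve using SCS recorded after treatment discontinuation (collected under protocol 5.6.2). Restricting the 30-day proportion to patients with at least 30 days on treatment is not advised. It selects on post-randomisation duration and lifts the captured share only from 46, 19 and 6% to 50, 23 and 9% in the three shortest windows.

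Cost: a few extra descriptive outputs and reliance on non-informative censoring. OCS start and end dates (protocol 6.4.1) and biologic prescription dates (protocol 6.4.5) are already collected.
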